Title	Intravenous Remodulin (treprostinil) as Add-on Therapy for the Treatment of Persistent Pulmonary Hypertension of the Newborn: A Randomized, Placebo-Controlled, Safety and Efficacy Study
Study Phase	Phase II
Indication	Persistent Pulmonary Hypertension of the Newborn (PPHN)
Primary Objective	To explore the safety and treatment effect of intravenous (IV) Remodulin as add on therapy in neonates with PPHN compared to placebo. Efficacy will be assessed by a composite endpoint of clinical worsening through Day 14 as defined by one of the following: 
 • Death • Initiation of extracorporeal mechanical oxygenation (ECMO) per institutional policies • Need for additional treatment (initiation of an additional targeted pulmonary vasodilator therapy [e.g., phosphodiesterase-5 inhibitor [PDE-5i], endothelin receptor antagonist [ERA], prostacyclin, L-citrulline]])
Secondary Objectives	To assess the effect of IV Remodulin as add on therapy in neonates with PPHN compared to placebo in the following: 
 • Change in Oxygenation Index (OI) from Baseline to Hours 12, 24, 72, Days 7 and 14 and/or prior to study drug discontinuation/weaning • Change in $\text{PaO}_2 / \text{FiO}_2$ (P/F ratio) from Baseline to Hours 12, 24, 72 • Change in pre- and post-ductal oxygen saturation (SpO_2) from Baseline to Hours 6, 12, 24 and 72 • Time to discontinuation of inhaled nitric oxide (iNO) • Time on mechanical ventilation • Time to initiation of ECMO • Time to clinical worsening • Change in N-terminal pro-Brain Natriuretic Peptide (NT-proBNP) • Safety (adverse events (AEs), clinical laboratories, and physical exam findings)
	To evaluate treprostinil pharmacokinetics in neonates with PPHN
Study Design	Randomized, double-blind, placebo-controlled, multi-center, comparative study
Sample Size	The study may enroll approximately 70 subjects to ensure at least 66 evaluable subjects; no more than 32 evaluable subjects with a diagnosis of PPHN associated with congenital diaphragmatic hernia (CDH) will be enrolled.

Summary of Subject Eligibility Criteria	Eligible subjects will be at least 34 weeks gestational age, 2 kg at screening and have a diagnosis of PPHN. The subject must have two consecutive OIs of 15 or greater, separated by at least 30 minutes, after having received iNO for at least 3 hours prior to randomization and initiation of study drug.
Drug Dosage and Formulation	
Study drug (Remodulin or matching placebo) will be supplied in 20mL clear glass vials containing 1mg/mL treprostinil or placebo. Each vial must be discarded within 30 days after first opening. A new vial should be used for each subject.
 
Study drug must be diluted with high-pH glycine diluent (Sterile Diluent for Remodulin, Sterile Diluent for Flolan, or Sterile Diluent for Epoprostenol Sodium), Sterile Water for Injection, or 0.9% Sodium Chloride Injection, prior to administration as a continuous intravenous infusion via an indwelling central venous catheter, using an infusion pump designed for intravenous drug delivery. If clinically necessary, a peripheral intravenous cannula may be used for short term administration of study drug. A dedicated IV line or port/lumen is required for the IV administration of study drug.

	
In the event dedicated central venous access cannot be established, or in the opinion of the Investigator the patient is too unstable to attempt to establish a dedicated central venous access line for IV administration of study drug, study drug may be initiated as a continuous subcutaneous (SC) infusion at the discretion of the Investigator. Subjects initiated on IV administration of study drug who lose venous access may be transitioned to SC administration.
 
Dilution of study drug is usually not required for continuous SC administration in an adult population; however, based upon the selected SC infusion pump flow rate capabilities, the subject's dose weight, and dose in this neonate patient population, dilution will likely be required for SC administration (especially for smaller babies and lower doses, or during weaning of study drug). If dilution is required for SC administration, Sterile Water for Injection or 0.9% Sodium Chloride for Injection should be used.

The line should not be flushed to avoid an accidental over dosage.

Initiating study drug

Study drug will be initiated at 1ng/kg/min. The dose of study drug should be increased by up to 2ng/kg/min every 2 hours as tolerated and clinically indicated by the physician. As some subcutaneous infusion pumps may not accommodate a starting dose of exactly 1ng/kg/min, the site may proceed with a starting dose as close to 1ng/kg/min as possible. The initial starting dose should not exceed 2ng/kg/min and should be increased by approximately 1-2ng/kg/min every 2 hours as tolerated and clinically indicated by the physician.

Dose titration

The dose escalation should continue in up to 2ng/kg/min increments every 2 hours, as tolerated and clinically indicated by the physician, while the OI is ≥ 15 (or the FiO₂ requirement is $\geq 60\%$, if the OI is not calculated) in the absence of dose-limiting adverse events (e.g., due to systemic hypotension). When the OI is between 10-14 and the study drug dose is ≤ 10 ng/kg/min, the dose should continue to be increased; if the study drug dose is > 10 ng/kg/min and the OI is between 10-14, any further dose escalation will be left to the discretion of the clinicians/investigator according to the clinical condition of the subject, and the perceived need for additional pulmonary vasodilation.

The dosing of study drug is based upon the OI (as long as it is calculated) and then by the FiO₂ as needed. Suggested dose titration parameters are listed in the table below.

OI	FiO₂ (To be used when OI is not calculable)	Dosing Strategy
≥ 15	$\geq 60\%$	Dose increase, as tolerated
10-14	--	
Current Remodulin dose > 10ng/kg/min
 
Hold dose or dose increase if clinical condition warrants further pulmonary vasodilation.

10-14	--	
Current Remodulin dose ≤ 10ng/kg/min
 
Dose increase, as tolerated

<10	<60%	Begin weaning. The iNO should be weaned and discontinued prior to initiating weaning of study drug.

Dose maintenance

Once the target therapeutic goal has been reached (i.e., OI < 10 or FiO₂ $< 60\%$) the current dose of study drug should continue for at least 12 hours prior to beginning to wean study drug.

Dose Wean

Down titration will begin once the subject is no longer receiving iNO and the OI is < 10 (or the FiO₂ is $< 60\%$ if the OI is not calculated); iNO should be weaned and discontinued prior to initiating weaning of study drug.

It is recommended the dose of study drug be decreased by no more than 10ng/kg/min per day (in divided increments, either in the same manner as the dose was increased or as determined by the Investigator). Faster weaning may occur if required per subject care.

Subjects who have residual or chronic pulmonary hypertension that does not fully resolve by Day 14 may continue to receive study drug for up to an additional 14 days (for a total of up to 28 days) per the Investigator's discretion, if clinically indicated.

Control Group	Placebo
Route of Administration	Continuous intravenous infusion; administration as a continuous subcutaneous infusion may be used in subjects in whom dedicated central venous access cannot be established, who are too unstable to attempt to establish a dedicated central venous access line for IV administration of study drug, or for subjects initiated on an IV infusion of study drug who lose venous access.
Procedures	Once parental or legal guardian consent has been provided, the subject will undergo the appropriate screening procedures to determine eligibility. After the inclusion/exclusion criteria have been confirmed, the subject will be enrolled and randomized via the IWRS.

Study drug initiation and administration phase

- First 72 hours
 - Vital signs and OI assessments will occur approximately every six hours (6 ± 2 hours) while on study drug.
 - BP, HR and SpO₂, and doses of inotropes will also be collected with each study drug dose change.
 - Physical examination and NT-proBNP will be collected daily for the first 72 hours.
 - After 24 hours (+6 hours) on study drug, one blood sample will be collected for pharmacokinetic (PK) analysis.
- Day 4 throughout duration of study drug treatment
 - Assessments will occur at least once daily including vital signs, FiO₂, blood gasses, and OI assessment.
 - BP, HR, SpO₂ and doses of inotropes will also be collected with each study drug dose change.
- Day 7 and Day 14
 - In addition to the daily assessments, physical examination, clinical laboratory assessments, echocardiogram, and NT-proBNP will be performed.

Study drug weaning and discontinuation

- Immediately prior to weaning study drug
 - Key assessments include physical examination, vital signs, clinical laboratory assessments, echocardiogram, OI assessment, FiO₂, NT-proBNP, inotrope support, and PK sample collection.

- Every 24 hours while weaning
 - Assessments will occur once each day while weaning study drug and include vital signs, physical examination, FiO₂, and mean airway pressure (MAP) if still on mechanical ventilation.
 - BP, HR, SpO₂, FiO₂, and doses of inotropes will also be collected with each study drug dose change.

Follow-up

- Within 12 hours after last dose of study drug
 - Physical examination, vitals, FiO₂, blood gasses, MAP, clinical laboratory assessments, and NT-proBNP
- 48 hours after the last dose of study drug
 - Vitals, clinical laboratory assessments, and echocardiogram
- Post-treatment data will be collected until subject is withdrawn from the study, death, time of hospital discharge, or until 4 weeks after last dose of study drug, whichever comes first.
 - The following key assessments will occur at time of withdrawal from study, hospital discharge, or at 4 weeks after last dose of study drug, whichever comes first: physical exam, vital signs, and clinical laboratory assessments.
 - Additionally, time on mechanical ventilation, time on inhaled iNO, and time of initiation of EMCO (if applicable) will be recorded.
 - The subject's participation in the study will conclude at the time of hospital discharge, death, withdrawal from the study, or at 4 weeks after last dose of study drug, whichever comes first.
 - Subjects with ongoing AEs at the time of study withdrawal or hospital discharge will continue to be followed for their AEs until either resolution (or return to normal or Baseline values), until judged by the Investigator to no longer be clinically significant, or until 4 weeks after last dose of study drug. All SAEs will be followed until resolution, death, or the subject is lost to follow-up, even if they are ongoing more than 4 weeks after the last dose of study drug.

Statistical Considerations	Based on the systematic review of use of nitric oxide for respiratory failure in infants by Finer and Barrington, 57.9% (194/335) subjects in the control group had an outcome of death or requirement for EMCO. In this study, assuming 60% subjects in placebo group and 30% subjects in Remodulin group with an outcome of death, requirement for EMCO, or need for additional PAH therapy, we calculated that 66 subjects (33 subjects per treatment group) will have at least 80% power to show a significant difference in favor of Remodulin at alpha level of 0.05 (one-sided test).
-----------------------------------	--

Approximately seventy subjects are planned to be randomized (1:1) to either receive treatment with Remodulin or placebo on top of the standard of care.

Sponsor United Therapeutics Corp.
 [name]
 [name]
 [name]

TABLE OF CONTENTS

LIST OF CONTACTS FOR STUDY	2
INVESTIGATOR'S AGREEMENT	3
PROTOCOL SYNOPSIS	4
TABLE OF CONTENTS.....	10
Table of In-text Tables.....	14
Table of In-text Figures	14
LIST OF ABBREVIATIONS	15
1 BACKGROUND AND RATIONALE	17
1.1 DEFINITION OF CLINICAL PROBLEM.....	17
1.2 REMODULIN (TREPROSTINIL) BACKGROUND	18

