^bThe Day 4 and the 72 hour time point assessment will fall on the same calendar day. A separate set of assessments should be captured for the Day 4 assessment. Day 7 and Day 14 assessments should be performed even if the subject has discontinued study drug. If subjects are discharged from the hospital prior to study Day 14, Day 14 assessments should be completed prior to hospital discharge. Subjects may receive up to 28 days of study drug.

^cHospital discharge or 4 weeks after discontinuation of study drug (whichever comes first).

^dVital signs include BP, HR, RR, temperature, and SpO₂. SpO₂ will be collected both pre- and post-ductal for the first 72 hours. BP, HR, and SpO₂ will be collected with each study drug dose change.

^eOI will be calculated as long as the subject is on mechanical ventilation and arterial blood gasses (ABGs) are collected.

^fCollected for as long as the subject is on mechanical ventilation.

^gABGs will be collected as long as the subject has arterial access. Venous or capillary blood gas will be collected thereafter. Lactate will be drawn with each blood gas.

^hClinical labs include: chemistries, hematology, and liver function tests. Performed by institutional laboratory.

ⁱIf subject had historic ECHO performed within 36 hours prior to time informed consent was signed, then ECHO does not need to be repeated at Screening. A ±2 day window for Day 7 and Day 14 ECHO.

^jClinical worsening is assessed from Baseline to the conclusion of Day 14 or hospital discharge, whichever comes first. Events occurring after Day 14 will not count towards the primary analysis of clinical worsening.

^k“Prior to wean” assessments will be collected after the dose has been maintained for at least 12 hours and no more than 1 hour prior to beginning to wean study drug. Assessments should be collected for subjects randomized to placebo; PK sample not required in subjects randomized to placebo. In the event that the subject will continue to receive Remodulin beyond Day 28, prior to wean assessments should take place on Day 28.

^lA single PK sample will be collected after 24+6 hours of study drug dosing. The dose should have been maintained for at least 2 hours prior to the sample collection time.

^mConcomitant medications will be captured up to 48 hours after the subject has stopped receiving study drug.

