3.3.1.2 *Oxygenation Index (OI)*

The OI is an assessment of how much oxygen diffuses across the membranes of the lungs and into the blood when a subject inhales. Higher OIs indicate an increased risk of poor subject outcomes because the subject is unable to get as much oxygen out of each breath. Typically when the OI is greater than 40, ECMO is considered. The OI is calculated as follows:

$$OI = [MAP(\text{mmHg}) \times \text{FiO}_2(\%) / \text{PaO}_2(\text{mmHg})] \times 100$$

An OI will be calculated at Screening, Baseline, approximately every 6 hours for the first 72 hours, daily starting on the fourth day of study drug for as long as the subject is on study drug, and within 1 hour prior to weaning study drug for as long as the subject has arterial access for collection of arterial blood gases (ABGs) and is on mechanical ventilation (Table 3-1). An OI will be collected on study Day 7 and Day 14 (as long as the subject has arterial access for collection of ABGs and is on mechanical ventilation) regardless if the subject has already been weaned from study drug.

The OI should be used to guide study drug dosing. When the OI cannot be calculated (i.e., no arterial access for ABGs and/or subject not on mechanical ventilation), FiO_2 will be used to guide dosing (per Section 6.1.3).

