3.3.1.5 Blood Gas and Lactate

Blood gas (arterial, capillary, or venous) values will be collected at Screening, Baseline, every 6 hours for the first 72 hours, then daily starting on the fourth day of study drug for as long as the subject is on study drug. Additionally, blood gases will be assessed within 1 hour prior to weaning and at the time of study drug discontinuation. Blood gases will be assessed on study Day 7 and Day 14 regardless if the subject has already been weaned from study drug.

The ABGs should be collected from a post-ductal artery when possible. If a post-ductal arterial catheter is not available, it should be noted in the eCRF that the ABG was collected from a pre-

ductal artery. The ABGs will include: PaO₂, partial pressure of arterial carbon dioxide (PaCO₂), bicarbonate (HCO₃), oxygen saturation (SaO₂), and pH.

Capillary or venous blood gasses (CBGs or VBGs) will be collected when the subject no longer has arterial access. The CBG or VBGs will include: partial pressure of venous oxygen (PvO₂), partial pressure of venous carbon dioxide (PvCO₂), HCO₃, oxygen saturation (SvO₂), and pH.

Table 3-2 Blood Gasses

Blood Gasses	
Arterial	Capillary/ Venous
PaO ₂	PvO ₂
PaCO ₂	PvCO ₂
HCO ₃	HCO ₃
SaO ₂	SvO ₂
pH	pH

A blood lactate level will be collected with each blood gas.

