3.3.2.2 Vital Signs

Vital signs will include blood pressure (BP), heart rate (HR), respiratory rate (RR), temperature (temp), and oxygen saturation (SpO₂). Both pre- and post-ductal SpO₂ will be collected for the first 72 hours. Vital signs will be collected at Screening, Baseline, and during study drug administration as follows: approximately every 6 hours for the first 72 hours, daily starting on the fourth day for as long as the subject is on study drug, prior to weaning, every 24 hours while weaning, at the time of study drug discontinuation, and 48 hours after study drug discontinuation. Vital signs will also be collected prior to hospital discharge or at the 4 week follow-up after discontinuing study drug, whichever comes first. Additionally, BP, HR, and SpO₂ will be collected with each study drug dose change.

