6.2 ACCESS TO BLINDED TREATMENT ASSIGNMENT

In the event of a medical emergency that requires immediate unblinding, an unblinding call may be made to determine treatment assignment. The identity of a subject's treatment assignment, should it need to be obtained, will occur through an unblinding call to the 24 hour [REDACTED]

[REDACTED]. Investigators will be permitted to access the treatment assignment upon the subject meeting the criterion for clinical worsening or after the completion of Day 14 if required for purposes of medically managing the subject (e.g., another prostacyclin will be initiated). Subjects randomized to placebo may be discontinued from study drug at that time. Subjects randomized to Remodulin who have residual or chronic pulmonary hypertension that does not fully resolve by Day 14 may continue to receive study drug for up to an additional 14 days (for a total of up to 28 days) per the Investigator's discretion. Subjects who have PPHN resolved by Day 14, who have already begun weaning by Day 14 or for whom it is anticipated that weaning of study drug will begin within

shortly after completing Day 14, or who are withdrawn from the study should remain blinded. All attempts should be made to maintain the blind during the study.

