7.3 TREATMENT PHASE

7.3.1 *First 72 Hours*

The following assessments will be obtained during the first 72 hours of study drug administration.

- Physical examination (once daily)
- Vital signs approximately every 6 hours (BP, RR, HR, Temp, pre- and post-ductal SpO₂)
- OI assessment approximately every 6 hours (as long as the subject is on mechanical ventilation and ABGs are obtained)
- FiO₂; approximately every 6 hours
- MAP approximately every 6 hours (as long as the subject is on mechanical ventilation)
- Blood gases approximately every 6 hours (ABG if possible, otherwise CBGs/VBGs)
- NT-proBNP (once daily)
- Record concomitant medications
- Continue study drug, up-titrating as needed
 - BP, HR, and SpO₂ will also be collected with each study drug dose change
 - Record doses of inotropes with each study drug dose change
- Record AEs
- Collect PK sample 24 hours after the start of study drug dosing. Sample should be collected at least 2 hours after the last dose change (See Section 3.3.3 and Appendix 15.2)
- Assess clinical worsening (throughout the 14 day study period)

7.3.2 *Study Day 4 Throughout Duration of Study Drug Therapy*

The following assessments will be obtained daily starting on the fourth day of study drug administration and continue throughout the duration of study drug therapy:

- Vital signs (BP, RR, HR, Temp, SpO₂)
- OI assessment (as long as the subject is on mechanical ventilation and ABGs are obtained)

- FiO₂
- MAP (as long as the subject is on mechanical ventilation)
- Blood gases (ABG if possible, otherwise CBGs/VBGs)
- Record concomitant medications
- Continue study drug, up-titrating as needed
 - BP, HR, and SpO₂ will also be collected with each study drug dose change
 - Record doses of inotropes with each study drug dose change
- Record AEs
- Assess clinical worsening (throughout the 14 day period)

Subjects who have residual or chronic pulmonary hypertension that does not fully resolve by Day 14 may continue to receive study drug for up to an additional 14 days (for a total of up to 28 days) per the Investigator's discretion.

7.3.2.1 Study Day 7 and Day 14

The following assessments should be performed on study Day 7 and Day 14 regardless if the subject has already been weaned from study drug. If the subject will be discharged from the hospital prior to Day 14, the Day 14 assessments should be completed prior to hospital discharge.

- Physical examination
- Vital signs (BP, RR, HR, Temp, SpO₂)

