8.6 ASSESSMENT WINDOWS

For some assessments, target study day and time have been specified in the protocol. These scheduled assessments, as recorded on the eCRFs, and the corresponding target days and times and study days and time intervals are specified in [Table 8-2](#).

Table 8-2 Assessment Windows for Scheduled Assessments

Visit	Target Study Day/Time	Study Day/Time Interval
Echocardiograms:		
Day 7	Day 7	2 ≤ Study Day ≤ 9
Day 14	Day 14	10 ≤ Study Day
Vital signs, OI, FiO₂, Blood Gas/Lactate:		
Hour 6	Day 1/6 hours	1 ≤ Study Day 1, Hour 6 ≤ 9
Hour 12	Day 1/12 hours	10 ≤ Study Day 1, Hour 12 ≤ 15
Hour 18	Day 1/18 hours	16 ≤ Study Day 1, Hour 18 ≤ 21
Hour 24	Day 1/24 hours	22 ≤ Study Day 1, Hour 24 ≤ 27
Hour 30	Day 2/6 hours	28 ≤ Study Day 2, Hour 6 ≤ 33

Visit	Target Study Day/Time	Study Day/Time Interval
Hour 36	Day 2/12 hours	34 ≤ Study Day 2, Hour 12 ≤ 39
Hour 42	Day 2/18 hours	40 ≤ Study Day 2, Hour 18 ≤ 45
Hour 48	Day 2/24 hours	46 ≤ Study Day 2, Hour 24 ≤ 51
Hour 54	Day 3/6 hours	52 ≤ Study Day 3, Hour 6 ≤ 57
Hour 60	Day 3/12 hours	58 ≤ Study Day 3, Hour 12 ≤ 63
Hour 66	Day 3/18 hours	64 ≤ Study Day 3, Hour 18 ≤ 69
Hour 72	Day 3/24 hours	70 ≤ Study Day 3, Hour 24
PK Assessments		
After 24 hours of study drug dosing	Day 1	24 hours ± 12 hours

Abbreviations: FiO₂, fraction of inspired oxygen; OI, oxygenation index; PK, pharmacokinetic(s)

Note: Study Day = (Assessment Date) - (First Dosing Date) +1

For assessments that are not listed in [Table 8-2](#), the nominal assessment name recorded in the eCRF will be used.

Multiple Evaluations Within the Same Analysis Window

After all the observations have been slotted based on the specifications above, if there are multiple valid observations for an assessment within an assigned analysis visit window, only 1 of these observations will be used for summary statistics and analyses. The observation to be used is determined using the following hierarchy (in decreasing order):

- The observation closest to the target study day and time
- The later observation if 2 observations are equally close to the target study day and time

For missing values where the LOCF algorithm is applied, it is always the last valid observation on treatment carried forward, even though this might not be the observation obtained by the above hierarchy and used in the summaries by visit window.

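### Hour 6 to 72 readings are tied to study drug in some protocol sections but not others, so Hour 72 (and some Hour 24) secondary endpoint values can be missing by arm and outcome

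*Protocol*

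**What the plan says.** **Readings tied to study drug.** The synopsis (Procedures, first 72 hours) states: "Vital signs and OI assessments will occur approximately every six hours (6 ± 2 hours) while on study drug". Protocol 7.3.1 lists OI, FiO2, mean airway pressure (MAP), blood gas and pre-/post-ductal SpO2 under the line "The following assessments will be obtained during the first 72 hours of study drug administration". Section 3.3.2.2 collects vital signs, which include SpO2, "during study drug administration as follows: approximately every 6 hours for the first 72 hours".

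**Readings with no such condition.** Section 3.3.1.2 says "An OI will be calculated at Screening, Baseline, approximately every 6 hours for the first 72 hours", and attaches the on-drug phrase only to the daily schedule from the fourth day. Sections 3.3.1.3 (MAP) and 3.3.1.4 (FiO2) are built the same way. Section 3.3.1.5 sets blood gas "every 6 hours for the first 72 hours, then daily starting on the fourth day of study drug".

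**Express off-drug rule.** This exists only for the later visits. Table 3-1, footnote b: "Day 7 and Day 14 assessments should be performed even if the subject has discontinued study drug".

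**Unblinding and stopping.** Protocol 6.2 allows the code to be opened once an infant meets clinical worsening, if medical management requires it, and adds: "Subjects randomized to placebo may be discontinued from study drug at that time". Section 4.3.1.2 lets infants who worsen continue study drug for up to 28 days in total. Table 3-1, footnote p, drops the daily weaning readings for infants unblinded and found to be on placebo.

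**Analysis.** OI and P/F are compared at Hours 12, 24 and 72, and SpO2 also at Hour 6. Missing continuous values take LOCF, and under SAP 8.6 "it is always the last valid observation on treatment carried forward". SAP 10.2.1 also plans the OI analysis without imputation. P/F and SpO2 are to be handled similarly.

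**The concern.** The fixed-hour endpoints need a reading at that hour from every infant who can provide one. If sites follow the synopsis and 7.3.1, an infant who stops study drug before Hour 72 leaves the 6-hourly schedule. The unblinding rule makes that exit depend on two things at once: the infant has worsened, and the infant was on placebo.

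The carried value is then likely to be a bad one. Under 3.3.1.1.1, added vasodilator therapy requires an OI above 20. Before 24 hours on study drug it also requires two OIs above 30 or two arterial lactates of at least 4 mmol/L. The last on-treatment OI of a stopped placebo infant therefore sits near the moment of failure. A Remodulin infant with the same course who continues is measured later, after rescue therapy has had time to act. If rescued infants improve, the Hour 72 comparison is tilted towards Remodulin even when the drug has no effect on oxygenation. The unimputed analysis leaves the stopped placebo infants out, which can tilt the comparison the other way. Neither analysis recovers the missing value.

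**Working it through.** **1. Plan's own figure.** Inputs from Protocol 10.2: 60% versus 30%, one-sided alpha 0.05, 80% power. With pooled variance under the null and no continuity correction:

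n per arm = [1.645 × √(2 × 0.45 × 0.55) + 0.842 × √(0.60 × 0.40 + 0.30 × 0.70)]² / 0.30² = 32.9, so 33 per arm and 66 in total, with power 80.1%. The stated size reproduces. Only the 60% and the 33 are used below.

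**2. Which hours are exposed.** Added therapy normally requires 24 hours on study drug. Earlier use needs the stricter OI or lactate criteria. Hour 12 is therefore barely exposed, Hour 24 somewhat, and Hour 72 most.

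**3. What the post-stop visits supply.** Section 7.3.3.3 requires vital signs, FiO2, MAP if ventilated, and blood gas within 12 hours of stopping. Section 7.3.3.4 requires vital signs at 48 ± 4 hours, with no blood gas, FiO2 or MAP. SAP Table 8-2 sets the Hour 24 window at 22-27 hours and starts the Hour 72 window at 70 hours.

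- Stop at Hour 20: the first set falls at Hours 20-32 and may or may not land in 22-27. The second falls at 20 + 44 to 20 + 52 = Hours 64-72, so SpO2 may land in the Hour 72 window. OI and P/F cannot, because no gas is taken.
- In general, the set containing a blood gas can reach Hour 70 only if the stop is at Hour 70 − 12 = 58 or later. For earlier stops, these visits give no Hour 72 OI or P/F.

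**4. How many infants.** The documents do not split the 60% into death, ECMO and added therapy, and do not say when events occur or how often placebo is stopped. Assumptions: share of events that are added therapy *a*; share of those before Hour 72, 0.50-0.80; share of those infants unblinded and stopped, 0.25-0.75.

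Affected = 33 × 0.60 × *a* × (0.50 × 0.25 to 0.80 × 0.75) = 19.8 × *a* × (0.125 to 0.60)

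| *a* | Placebo infants affected, of 33 |
|---|---|
| 0.50 | 9.9 × 0.125 = 1.2 to 9.9 × 0.60 = 5.9 |
| 0.25 | 4.95 × 0.125 = 0.6 to 4.95 × 0.60 = 3.0 |
| Only the excess of 60% over the cited 57.9% for death or ECMO | 33 × 0.021 × (0.125 to 0.60) = 0.1 to 0.4 |

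Remodulin infants leaving by this route: none if all continue.

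**5. Effect on the mean.** Shift in the placebo mean = share affected × (carried OI − true Hour 72 OI). At *a* = 0.50 the share is 1.2375/33 = 3.75% to 5.94/33 = 18%. If the gap is 10-15 OI units (an assumption with no source in the documents), the shift is 0.0375 × 10 = 0.4 to 0.18 × 15 = 2.7 units. If the rescued infants have not improved by Hour 72, it is zero.

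**The case against.** The strongest reply is that the protocol already schedules these readings. Sections 3.3.1.2 to 3.3.1.5 give 6-hourly OI, MAP, FiO2 and blood gas for 72 hours with no on-drug condition. Section 3.3.2.2 and Table 3-1, footnote d, say in general terms that pre- and post-ductal SpO2 is collected for the first 72 hours. Section 8.1 asks for every effort to complete scheduled evaluations after premature discontinuation. This stands as far as it goes. It shows that the protocol contradicts itself, and a site following 7.3.1 would be entitled to stop. Section 8.1 does not settle the matter, because it covers only what is scheduled.

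Second, each step is optional. The code is opened only if management requires it, stopping placebo is permitted and not required, the blind is to be kept where possible, and 6.1.5 says ECMO should not normally lead to unblinding. This stands, and it keeps the number small.

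Third, the secondary tests run only if the primary is significant and are called exploratory (SAP 8.4). This also stands and limits the consequence. It does not remove the imbalance, because a significant result in favour of Remodulin means that placebo has more worsening events.

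A reader might infer that Hour 12 to 72 values are missing by arm as a built-in feature of the design, or apply the whole 60% event rate and reach 19.8 × 0.60 = 11.9 of 33 infants. The documents do not support either. The loss is possible, not prescribed. The 60% includes death and ECMO, which are not this route. A false-positive rate for the t-test would also need an SD and an OI gap that the documents do not give.

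**Conclusion.** The concern holds in a limited form. The protocol is inconsistent on whether Hour 6 to 72 readings continue after study drug stops. Combined with the unblinding rule, this lets values, mainly at Hour 72 and to a lesser extent at Hour 24, go missing according to arm and outcome. On-treatment LOCF then tends to fix stopped placebo infants at a poor value. The discontinuation visits recover some data, especially SpO2, but do not reliably supply an Hour 72 OI or P/F.

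The size is about 1 to 6 of 33 placebo infants under the stated assumptions, and fewer if most placebo events are ECMO or death. The direction for LOCF rests on rescued infants having improved by Hour 72. The primary endpoint is not affected. This is an inexpensive improvement to exploratory secondary endpoints and not a threat to the main result.

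**What to change.** **Protocol.** Reconcile the synopsis, Table 3-1, Section 3.3.2.2 and Section 7.3.1 with Sections 3.3.1.2 to 3.3.1.5. State that OI, FiO2, MAP, blood gas and pre-/post-ductal SpO2 at Hours 6 to 72 are recorded through Hour 72 whether or not study drug has been stopped, using values available from ICU care, as is already done for Day 7 and Day 14. The existing limits stay: OI needs ventilation and arterial gases.

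**SAP 8.6.** Confirm in one sentence that an observed off-drug value inside the window is used before any carry-forward. Table 8-2 places values by time and already implies this, but the on-treatment wording of the LOCF rule leaves room for doubt.

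The same change covers infants weaned before Hour 72, who also leave an on-drug schedule, possibly more often in the Remodulin arm.

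**Cost.** A protocol wording change, one SAP sentence, and a few more eCRF entries for infants stopped early. Nothing about treatment, unblinding or stopping needs to change.
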